Numeric pain rating scale (NPRS) was used to determine the level of the participant's pain. It consists of a straight 100 mm line that is scored from 0 to 10 with 10 mm intervals. The zero represents no pain while a 10 represents very severe pain. The Numeric pain rating scale has moderate reliability with correlation coefficients ranging from 0.60 to 0.77 ²⁶. In addition, Boonstra, Preuper, Reneman, Posthumus, Stewart ²⁶ indicated that NPRS has high validity in detecting pain with correlation coefficients ranging from 0.64 to 0.84.

Neck Disability Index

The Neck Disability Index (NDI) consists of ten items that each range from 0 to 5 that help measure the level of disability for patients with neck pain. The NDI score ranges from 0 to 50 ²⁷. The level of disability determined by the score of NDI is as follows: 0 - 4 = no disability, 5 - 14 = mild, 15 - 24 = moderate, 25 - 34 = severe, and above 34 = complete disability ²⁷. The NDI has a high test-retest reliability with an intra class correlation (ICC) between 0.88 and 0.95 and high internal consistency with Cronbach's α values ranging from 0.85 to 0.90 ²⁸. For NDI score, the ICC was 0.83 (95% CI, 0.75–0.90), which indicates that the NDI has high validity to detect any

small change in the patient's condition²⁹. In addition, Childs, Cleland, Elliott, Teyhen, Wainner, Whitman, Sopky, Godges, Flynn, Delitto¹⁸ reported that NDI has high sensitivity and specificity of 0.83 and 0.72, respectively.

Global rating of change

The Global Rating of Change was used to measure the amount of improvement that the patient achieves from the intervention or rehabilitation program. The score ranges from -7 to 7 in which -/+3 to -/+ 1 represents a small change, -/+ 4 to -/+5 represents moderate change and -/+6 to -/+7 means a large change. The negative and positive signs determine whether the patient's condition worsens or improves respectively. GROC has a high test-retest reliability with an ICC value of 0.90 (95% confidence interval (CI) 0.84 to 0.93). In addition, GROC has high face validity with Pearson's $r = 0.72 - 0.90$ and $ICC = 0.74$ ³⁰. Kamper, Maher, Mackay³⁰ reported that the GROC has high construct validity when compared to other gold standard measurements such as the Roland Morris, Oswestry, and pain rating scale.

Procedures:

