The cervical mobilization and stretching exercise techniques were performed by a licensed physical therapist who has 6 years of experience in manual physical therapy.

Self-administered stretching exercises were performed by participants in the combined intervention group to the following muscles: the extensor muscles, the upper part of the trapezius, and the posterior scalene ⁶. Each movement was held for 30 seconds and repeated 3 times. Lastly, the participant was instructed to perform a neck straightening exercise by retracting the neck (Chin tuck) 5 times for 3-5 seconds. Subjects in the combined intervention group were provided with written instruction of the stretching exercises and directed to perform stretching exercise 5 times a week, each exercise session takes about 10 minutes. Patients were also instructed to keep a stretching diary to track their stretch exercise frequency.

Data collection:

Data was collected at baseline, one week after intervention, and week 4. The final data collection date was set at week 8 as a follow up to determine whether the participant was able to maintain gains at one month following the interventions.

Statistical Analyses

A sample size of 50 participants was estimated using a moderate effect size of 0.25, level of significance 0.05, and power of 0.80. Data was summarized using mean and standard deviation ¹ for quantitative variables and counts (%) for qualitative variables. The normality of continuous variables was examined using Shapiro Wilk's test. The distribution of the participants' characteristics by study group were evaluated using chi-square for qualitative variables and independent t- test for quantitative variables. Mixed factorial analysis of variance (ANOVA) was used to examine changes in cervical ROM variables, pressure pain threshold, NPRS, GROC, and NDI scores by study group over time. Post hoc comparisons using Bonferroni test and effect size were computed to identify significant differences over time. We compared percent change (4 weeks vs. baseline) for all outcome variables between the two study groups using independent t- test and Mann- Whitney test. To examine whether there were any changes in the outcome variables at 4 weeks follow up paired t- test was used. The level of significance was set at $p \leq 0.05$. Statistical analysis was performed using IBM SPSS Software version 24 for Windows (Chicago, IL, USA).

Results

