Thirty-eight (38) subjects with a mean \pm SD age 30.9 ± 8.1 years and body mass index (BMI) 26.8 ± 6.7 kg/m² participated in the study. Sixty- five percent of the participants were females (n=

26). There was no significant difference between the two study groups in terms of age, Body Mass Index (BMI), cervical ROM and pressure pain threshold at baseline. Demographic and general characteristics are presented in **Table 1**.

Changes in ROM

Results of the mixed factorial ANOVA for ROM is displayed in **Table 2**. There was a significant difference in mean ROM during extension over time ($F_{2,72}=6.8$, $p=0.002$, $\eta^2=0.20$), and a significant group by time interaction ($F_{2,72}=3.6$, $p=0.02$). Bonferroni post hoc comparison revealed that the difference was significant between baseline and one week later (70.2 ± 2.1 vs. 74.3 ± 2.4 , $p=0.04$), baseline and 4 weeks later (70.2 ± 2.1 vs. 76.6 ± 2.0 , $p=0.001$), however, there was no significant difference between one week later and 4 weeks ($p=0.15$). In addition, the % improvement from baseline to 4 weeks later was significantly different between the combined intervention and standard intervention groups respectively (18.9% vs. 3.0% ; $t=2.4$, $p=0.02$). (Refer to **Table 2**)

Also, there was a significant difference in mean ROM during right lateral flexion over time ($F_{2,72}=13.8$, $p<0.001$, $\eta^2=0.30$), and a significant group by time interaction ($F_{2,72}=2.9$, $p=0.04$). Bonferroni post hoc comparison revealed that the difference was significant between baseline and one week later (40.8 ± 1.5 vs. 43.8 ± 1.3 , $p=0.03$), baseline and 4 weeks later (40.8 ± 1.5 vs. 46.8 ± 1.4 , $p<0.001$), and between one week later and 4 weeks (43.8 ± 1.3 vs. 46.8 ± 1.4 , $p=0.001$). In addition, the % improvement from baseline to 4 weeks later was significantly different between the combined intervention and groups respectively (23.2% vs. 10.8% ; $t=1.8$, $p=0.04$). (Refer to **Table 2**).

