There was a significant difference in mean ROM during left lateral flexion over time ($F_{2,72}=3.0$, $p=0.03$, $\eta^2=0.30$), and a significant group by time interaction ($F_{2,72}=3.0$, $p=0.03$). Bonferroni post hoc comparison revealed that the difference was significant between baseline and one week later (43.0 ± 1.1 vs. 46.3 ± 1.0 , $p=0.01$), baseline and 4 weeks later (43.0 ± 1.1 vs. 48.5 ± 1.3 , $p<0.001$), and between one week later and 4 weeks (46.3 ± 1.0 vs. 48.5 ± 1.3 , $p=0.01$). In addition, the percent improvement from baseline to 4 weeks later was significantly more for the combined intervention as compared to the standard intervention group (20.0% vs. 7.7% ; $t=2.1$, $p=0.02$).

For the other ROM directions, flexion, right rotation, and left rotation, both groups had a significant improvement in mean ROM over time ($p<0.05$), however, this improvement was not significantly different between the two groups. (Refer to **Table 2**).

Change in Pressure Pain Threshold (PPT)

There was a significant difference in mean right upper trapezius muscle pressure pain threshold over time ($F_{2,72}=4.3$, $p=0.02$, $\eta^2=0.11$), however, there was no significant group by time

interaction ($F_{2,72}=0.98$, $p=0.38$), and the change over time was not significantly different between the two groups ($F_{2,72}=0.02$, $p=0.90$). Bonferroni post hoc comparison revealed that the difference was significant between baseline and 4 weeks later (4.7 ± 0.3 vs. 5.5 ± 0.3 , $p=0.01$), and between one week later and 4 weeks (4.7 ± 0.3 vs. 5.5 ± 0.3 , $p=0.01$). For left pressure pain threshold, there was a significant difference over time ($F_{2,72}=8.4$, $p=0.001$, $\eta^2=0.20$), however, there was no significant group by time interaction ($F_{2,72}=0.48$, $p=0.59$), and the change over time was not significantly different between the two groups ($F_{2,72}=0.02$, $p=0.86$). Bonferroni post hoc comparison revealed that the difference was significant between baseline and 4 weeks later (4.5 ± 0.3 vs. 5.7 ± 0.4 , $p=0.005$), and between one week later and 4 weeks (4.5 ± 0.2 vs. 5.7 ± 0.4 , $p=0.001$). (Refer to **Table 3**).

Changes in NPRS

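### The week-4 group difference is reported as percent change from baseline; for range of motion this loses power and lets chance baseline imbalance into the estimate, which adjusting for the recorded baseline would avoid.

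*Combined protocol and SAP*

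**What the plan says.** The Statistical Analyses section gives two between-group analyses. The first is a mixed model on raw scores: "Mixed factorial analysis of variance (ANOVA) was used to examine changes in cervical ROM variables" and the other outcomes. The second is the direct week-4 comparison: "We compared percent change (4 weeks vs. baseline) for all outcome variables between the two study groups", by independent t-test and Mann-Whitney test. Neither uses baseline as a covariate, although the Data collection section confirms it was recorded: "Data was collected at baseline, one week after intervention, and week 4".

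Under Changes in ROM, each positive claim carries a percent-change comparison. For extension (combined arm 18.9%, standard arm 3.0%; t=2.4) the text reads: "the % improvement from baseline to 4 weeks later was significantly different between the combined intervention and standard intervention groups respectively". For right lateral flexion the combined arm has 23.2% and the standard arm 10.8%, with t=1.8. For left lateral flexion (combined arm 20.0%, standard arm 7.7%; t=2.1) the text reads: "the percent improvement from baseline to 4 weeks later was significantly more for the combined intervention as compared to the standard intervention group". On balance, the Results describe the arms as having "no significant difference between the two study groups in terms of age, Body Mass Index (BMI), cervical ROM and pressure pain threshold at baseline".

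**The concern.** Dividing by baseline does not adjust for it. A participant who starts low by chance tends to regress upward, and the small denominator then enlarges the percentage. If percent change is negatively related to baseline, two things follow. Baseline variation adds noise to the group comparison, and an arm that happens to start lower shows a larger percent gain without any treatment effect. Regressing the week-4 value on baseline removes both, with data already in hand.

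With 18 and 20 participants analysed, a non-significant baseline test cannot rule out an imbalance large enough to matter. At stake is how the three ROM claims read, since no adjusted difference in degrees and no confidence interval appears in the text.

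There is also a wording problem. The plan covers every outcome, but for GROC, "The Global Rating of Change was used to measure the amount of improvement that the patient achieves from the intervention". It is a change score with no baseline, and its results begin at one week, so percent change is undefined for it.

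**Working it through.** **Inputs.** Arm sizes 18 and 20 (Procedures). Baseline and week-4 means with ± values, percent changes and t values (Changes in ROM). Tests are taken as two-sided at 0.05, because sidedness is not stated.

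**1. Reproduce the reported tests.** SE = gap / t; SD = SE / √(1/18 + 1/20) = SE / 0.325; CI = gap ± 2.028 × SE (36 df).

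| | Gap (points) | SE | SD | 95% CI | Two-sided p | Reported p |
|---|---|---|---|---|---|---|
| Extension | 18.9 − 3.0 = 15.9 | 6.6 | 20.4 | 2.5 to 29.3 | 0.022 | 0.02 |
| Right lateral flexion | 23.2 − 10.8 = 12.4 | 6.9 | 21.2 | −1.6 to 26.4 | 0.080 | 0.04 |
| Left lateral flexion | 20.0 − 7.7 = 12.3 | 5.9 | 18.0 | 0.4 to 24.2 | 0.043 | 0.02 |

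Extension reproduces. The two lateral-flexion p values match one-sided tests.

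**2. Are the ± values SEs or SDs?** If they were SDs, the SD of change could not exceed the sum of the two, so the SD of percent change would be at most about (2.1 + 2.0)/70.2 = 5.8, (1.5 + 1.4)/40.8 = 7.1 and (1.1 + 1.3)/43.0 = 5.6 points. Step 1 implies 18 to 21. They are therefore read as SEs, and baseline SD = SE × √38 = 12.9, 9.2 and 6.8 degrees.

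**3. Does percent change depend on baseline?** If it did not, the week-4 SE would be √{[((1+m)·SD₀)² + (mean₀·s)² + (SD₀·s)²]/38}, where m and s are the mean and SD of percent change as fractions (m = 0.105, 0.167, 0.135).

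- Extension: √[(204.8 + 204.9 + 7.0)/38] = 3.3; reported 2.0.
- Right lateral flexion: √[(116.5 + 74.8 + 3.9)/38] = 2.3; reported 1.4.
- Left lateral flexion: √[(59.2 + 60.1 + 1.5)/38] = 1.8; reported 1.3.

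The reported spread is too small for independence, so lower baselines go with larger percent gains. The implied baseline-to-week-4 correlations are about 0.53, 0.72 and 0.56.

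**4. Power.** Simulation with 20,000 trials per setting, 18 vs 20, these correlations, and an assumed true effect of 0.8 residual SD:

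| | Percent change | ANCOVA | Percent change, correlation 0.3–0.7 |
|---|---|---|---|
| Extension | 0.46 | 0.65 | 0.40–0.50 |
| Right lateral flexion | 0.44 | 0.65 | 0.35–0.44 |
| Left lateral flexion | 0.56 | 0.65 | 0.48–0.60 |

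Over the same range of correlations ANCOVA stays at about 0.66. Under a model that favours percent change (lognormal data, proportional effect), power is 0.49, 0.49 and 0.58 against 0.65. Simulated type I error is 0.040–0.049 for percent change and 0.049–0.051 for ANCOVA. For the neck disability index the gain is moderate (0.48–0.54 vs 0.60–0.62), and for the pain rating scale small (0.53–0.59 vs 0.60–0.62), both over assumed correlations of 0.3–0.7.

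**5. Imbalance.** One SE of the baseline difference is SD₀ × 0.325 = 4.2, 3.0 and 2.2 degrees. At the correlations in step 3 this moves the percent-change gap by about 4, 4 and 2.5 points. Varying the correlation gives slopes of 0.7–1.0, 1.5–1.7 and 1.1–1.4 points per degree, hence shifts of about 3–4, 4.5–5 and 2–3 points. The ANCOVA estimate moves by about zero.

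**The case against.** The strongest reply is that percent change is not the lead analysis. The mixed ANOVA is named first, each ROM claim opens with the group-by-time interaction, and percent change is added after it. Raw change from baseline to week 4, the scale of that ANOVA, has power of about 0.54, 0.58 and 0.62 in the same setting, so part of the gap is already recovered, most clearly for left lateral flexion. This stands as a limit on the size of the gain. It does not remove the point: the interaction compares unadjusted scores across three time points and yields no week-4 estimate.

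Other objections also bear on weight:

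- **The right lateral flexion interval.** It crosses zero because t=1.8 does not fit a two-sided p of 0.04. That is a separate inconsistency and would arise on any scale.
- **Which figures to trust.** If the reported p values are right and two-sided, the implied SDs for right and left lateral flexion fall to 17.9 and 15.6 and the correlations rise to about 0.83 and 0.67. Left lateral flexion power is then about 0.57 against 0.66. For extension, the Bonferroni p value suggests a correlation near 0.69 rather than 0.53. The direction is unchanged, but the second digit of the power figures is not firm.
- **No imbalance is demonstrated.** The arm-level tables are not in the available text, and a one-SE shift would not erase any of the three gaps.
- **Low power does not discredit a positive result.** True, since type I error holds. The concern for the positive claims is imprecision and conditional bias, not false positives in the long run.

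**Conclusion.** The concern holds, at moderate weight. For extension and right lateral flexion, percent change gives up roughly 20 points of power against ANCOVA (0.65 − 0.46 = 0.19; 0.65 − 0.44 = 0.21). For left lateral flexion it gives up about 9 (0.65 − 0.56), and the loss would be small if the true correlation were 0.8–0.9. A one-SE baseline imbalance would account for about a quarter of the extension gap (4/15.9), a third of the right lateral flexion gap (4/12.4) and a fifth of the left (2.5/12.3).

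These sizes rest on the assumed effect of 0.8 residual SD, on reading ± as SE, and on taking the reported t values as correct. The ranking of the two methods did not change under any variation tried. The size and direction of any actual imbalance cannot be judged from the available text, so it is unknown whether adjustment would strengthen or weaken the ROM claims.

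**What to change.** Replace the percent-change tests with ANCOVA of the week-4 value on group and that outcome's baseline, or take the same contrast from a baseline-adjusted mixed model. Report the adjusted difference with a 95% CI in original units (degrees for ROM). Compare raw week-4 GROC between arms. State which test applies to which outcome, rather than naming the t-test and Mann-Whitney test together for all. Base statements about differential improvement on the interaction or the adjusted contrast, not on the group main effect.

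Because the data have already been analysed, label this a post-hoc re-analysis and show it beside the existing result. The cost is rewording the statistical section and re-running existing data; nothing is asked of participants.

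### For every outcome with a baseline, the arms are tested at 0.05 by interaction and again on percent change, with no deciding test: the plan permits a per-outcome false-positive risk of about 7-11%

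*Combined protocol and SAP*

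**What the plan says.** Under Statistical Analyses, "Mixed factorial analysis of variance (ANOVA) was used to examine changes in cervical ROM variables, pressure pain threshold, NPRS, GROC, and NDI scores", with arm and visit as the two factors. Percent change from baseline to 4 weeks is then compared "for all outcome variables between the two study groups using independent t- test and Mann- Whitney test". The sentence beginning "The level of significance was set at" gives 0.05 as the single threshold.

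Two other sentences might have supplied a rule, but neither does:

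- "The normality of continuous variables was examined using Shapiro Wilk's test". No consequence is attached, so the check is not stated to select between the t-test and Mann-Whitney.
- "Post hoc comparisons using Bonferroni test and effect size were computed to identify significant differences over time". This adjustment covers comparisons between visits, not the several tests between arms.

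Under Changes in ROM, extension and right and left lateral flexion are each reported with a significant group-by-time interaction. Each is then followed by a percent-change t-test, also called significant. For extension the wording is "In addition, the % improvement from baseline to 4 weeks later was significantly different between the combined intervention and standard intervention groups".

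**The concern.** For a single outcome the plan produces two or three p-values that address much the same question: did the arms change differently? The interaction uses baseline, week 1 and week 4. Percent change uses baseline and week 4. The tests overlap heavily but not completely, so they can disagree, and the plan does not say what follows when they do.

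If any one of them is enough to claim an arm difference, 0.05 is not the error rate for that outcome. If agreement is required, the rate falls well below 0.05 and power is lost. Naming a primary outcome, or correcting across outcomes, would leave this open, because the named outcome would still have two or three p-values.

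**Working it through.** **The plan's own figure.** The documents give no per-outcome error rate beyond 0.05. The sample size of 50 (effect size 0.25, power 0.80) cannot be reproduced uniquely, because the test, the number of visits and the correlation are not stated. It plays no part in this point.

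**Inputs.**
- Arms of 18 and 20 (Procedures), matching the 38 completers.
- Three visits in the reported ANOVA, from the F statistics on 2 and 72 df (Changes in ROM).
- Degrees of freedom for the t-test: 18 + 20 − 2 = 36.
- Printed means, for example extension 70.2, 74.3, 76.6.
- Spread (assumption): the ± values are read as standard errors, so for extension SD ≈ 2.1 × √38 ≈ 12.9. Statistical Analyses says summaries are means and SDs, but the printed p-values do not fit that. If 2.1 and 2.4 were SDs, then even with zero correlation between visits the 4.1-degree change would have standard error √(2.1² + 2.4²)/√38 ≈ 0.52 and t ≈ 7.9. That is far from the printed p=0.04.
- Between-visit correlation (assumption): 0.3 to 0.85, compound symmetric or AR(1), with normal or lognormal data.

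**Reference under independence.** Two tests: 1 − 0.95² = 9.75%. Three tests: 1 − 0.95³ = 14.3%. The real tests are positively correlated, so their rates should lie between 5% and these values.

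**Null simulation.** No arm effect, 20,000 trials per setting, each test judged two-sided at p ≤ 0.05. Settings used the printed means for extension, right lateral flexion, PPT, NDI and NPRS.

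| Rule for claiming an arm difference | False-positive rate |
|---|---|
| Interaction alone | 4.6-6.1% |
| t-test alone | 3.8-5.2% |
| Mann-Whitney alone | 4.4-5.2% |
| t-test or Mann-Whitney | 5.4-6.6% |
| Interaction or t-test | 6.6-9.8% |
| Interaction or Mann-Whitney | 6.7-10.0% |
| Any of the three | 7.4-10.9% |

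For any of the three, the two ROM outcomes give 7.4-9.6%, PPT 7.5-9.2%, and NPRS and NDI 8.8-10.9%. Most of the excess comes from pairing the ANOVA with percent change, not from pairing the t-test with Mann-Whitney. In a narrower set of ROM settings (normal data, correlation 0.5-0.7), letting Shapiro-Wilk choose between t and Mann-Whitney still gives 7.7-7.9%. Requiring both interaction and t gives 2.1-2.3%.

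**Does the choice matter on the printed statistics?** With 2 numerator df, p = (1 + 2F/72)^(−36). The t-test is taken as two-sided on 36 df.

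| Outcome | Interaction F | Recomputed p | Printed p | t | Recomputed p | Printed p |
|---|---|---|---|---|---|---|
| Extension | 3.6 | 0.032 | 0.02 | 2.4 | 0.022 | 0.02 |
| Right lateral flexion | 2.9 | 0.061 | 0.04 | 1.8 | 0.080 | 0.04 |
| Left lateral flexion | 3.0 | 1.0833^(−36) = 0.056 | 0.03 | 2.1 | 0.043 | 0.02 |

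For left lateral flexion the two tests fall on opposite sides of 0.05. Rounding does not explain it: F from 2.95 to 3.05 gives p from 0.059 to 0.054, and t from 2.05 to 2.15 gives p from 0.048 to 0.038.

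One caution applies. The same F=3.0 is printed for the left lateral flexion time effect with η²=0.30. If that is partial η², F=3.0 implies only 2×3/(2×3+72) = 0.08. One of these entries may be a transcription error.

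**The case against.** The strongest reply is that the Results do not let any test win. Percent change appears in the text for three outcomes only, each time after an interaction reported as significant. PPT, NPRS and NDI have non-significant interactions, and none is rescued by percent change. If percent change is read only after a significant interaction, the per-outcome rate cannot exceed that of the interaction, about 5%. This stands as a description of the Results text. It is not a rule in the plan, which calls for percent change on all outcomes regardless.

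A second reply is that the t-test and Mann-Whitney are alternatives, chosen by normality. That is plausible: every percent-change result in the text is a t. The link is not written, however, and two tests still leave roughly 7-10%.

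Third, the sentences opening with an added percent improvement may be meant to convey the size of the effect. They also state significance, and a reader may take that as independent confirmation. It is not, since the two tests share the baseline and week-4 data. Nor are they computed from identical data, because the interaction also uses week 1.

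Fourth, there are 11 outcomes (six ROM directions, two PPT sides, NPRS, GROC, NDI) and no primary. One test each gives up to 1 − 0.95¹¹ = 43% under independence, so the per-outcome excess is the smaller problem. That is correct. It limits the priority of this point but does not answer it.

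**Conclusion.** The point holds as a gap in the plan. For the ten outcomes with a baseline, several between-arm tests share one 0.05 level and none is named as deciding. The permitted false-positive risk per outcome is about 7-11% if any test counts, and roughly 7-10% if Mann-Whitney is only a substitute. Both ranges depend on the assumed correlation and distribution and on the standard-error reading of the ± values.

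A reader might infer three stronger things that the documents do not support:

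- **That the risk has a fixed ceiling near 8.5%.** That is a mid-range value for ROM-type data. NPRS and NDI settings reach about 11%. Counting the group main effect, which the Results also report, as a fourth test would give about 11.8-14.0%.
- **That every outcome is affected.** GROC is itself a rating of change and is analysed on 1 and 36 df, that is, at two visits with no baseline. A percent change from baseline cannot be formed.
- **That the reported ROM differences are false positives found by choosing among tests.** No outcome in the Results text is claimed on percent change alone.

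Left lateral flexion shows that the choice can change a conclusion, provided its printed F and t are correct.

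**What to change.** In Statistical Analyses:

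- Name one two-sided between-arm test that decides for each outcome, for example the planned group-by-time interaction. State openly that the choice was made after results were known; it clarifies the claims but does not restore prospective error control.
- Keep one percent-change comparison, label it supportive, and attach no separate claim of significance. State when Mann-Whitney replaces the t-test, and exclude GROC.

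In the Results, reword the three sentences under Changes in ROM that present percent improvement as a further significant finding. Before relying on any of these results, recheck the printed interaction and t-test p-values against their F and t statistics, and state whether tests are two-sided. On the printed F values, right and left lateral flexion would not reach 0.05 by interaction (0.061 and 0.056).

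The cost is a few sentences in the analysis section, three reworded paragraphs and a check of existing output, with no new data. The downside is that an outcome significant only on the supportive test can no longer be claimed. Multiplicity across the 11 outcomes needs its own remedy.
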